12.3 Monitoring

Involvement in this study as a participating investigator implies acceptance of potential audits or inspections, including source data verification, by representatives designated by the DF/HCC Overall Principal Investigator (or Protocol Chair) or DF/HCC. The purpose of these audits or inspections is to examine study-related activities and documents to determine whether these activities were conducted and data were recorded, analyzed, and accurately reported in accordance with the protocol,

institutional policy, Good Clinical Practice (GCP), and any applicable regulatory requirements.

All data will be monitored for timeliness of submission, completeness, and adherence to protocol requirements. Monitoring will begin at the time of participant registration and will continue during protocol performance and completion.

13. REGULATORY CONSIDERATIONS

13.1. Protocol Review and Amendments

This protocol, the proposed informed consent and all forms of participant information related to the study (e.g., advertisements used to recruit participants) and any other necessary documents must be submitted, reviewed and approved by the DF/HCC IRB.

Any changes made to the protocol must be submitted as amendments and must be approved by the IRB prior to implementation. Any changes in study conduct must be reported to the IRB. The DF/HCC Overall Principal Investigator (or Protocol Chair) will disseminate protocol amendment information to all participating investigators.

All decisions of the IRB concerning the conduct of the study must be made in writing.

13.2. Informed Consent

All participants must be provided a consent form describing this study and providing sufficient information for participants to make an informed decision about their participation in this study. The formal consent of a participant, using the IRB approved consent form, must be obtained before the participant is involved in any study-related procedure. The consent form must be signed and dated by the participant or the participant's legally authorized representative, and by the person obtaining the consent. The participant must be given a copy of the signed and dated consent document. The original signed copy of the consent document must be retained in the medical record or research file.

13.3. Ethics and Good Clinical Practice (GCP)

This study is to be conducted according to the following considerations, which represent good and sound research practice:

- E6 Good Clinical Practice: Consolidated Guidance www.fda.gov/downloads/RegulatoryInformation/Guidances/UCM129515.pdf
- US Code of Federal Regulations (CFR) governing clinical study conduct and ethical principles that have their origin in the Declaration of Helsinki

- o Title 21 Part 11 Electronic Records; Electronic Signatures www.access.gpo.gov/nara/cfr/waisidx 02/21cfr11 02.html
- O Title 21 Part 50 Protection of Human Subjects www.access.gpo.gov/nara/cfr/waisidx 02/21cfr50 02.html
- O Title 21 Part 54 Financial Disclosure by Clinical Investigators www.access.gpo.gov/nara/cfr/waisidx_02/21cfr54_02.html
- O Title 21 Part 56 Institutional Review Boards www.access.gpo.gov/nara/cfr/waisidx 02/21cfr56 02.html
- o Title 21 Part 312 Investigational New Drug Application www.access.gpo.gov/nara/cfr/waisidx 02/21cfr312 02.html
- State laws
- DF/HCC research policies and procedures http://www.dfhcc.harvard.edu/clinical-research-support/clinical-research-unit-cru/policies-and-procedures/

It is understood that deviations from the protocol should be avoided, except when necessary to eliminate an immediate hazard to a research participant. In such case, the deviation must be reported to the IRB according to the local reporting policy.

13.4. Study Documentation

The investigator must prepare and maintain adequate and accurate case histories designed to record all observations and other data pertinent to the study for each research participant. This information enables the study to be fully documented and the study data to be subsequently verified.

Original source documents supporting entries in the case report forms include but are not limited to hospital records, clinical charts, laboratory and pharmacy records, recorded data from automated instruments, microfiches, photographic negatives, microfilm or magnetic media, and/or x-rays.

13.5. Records Retention

All study-related documents must be retained for the maximum period required by applicable federal regulations and guidelines or institutional policies.

14. STATISTICAL CONSIDERATIONS

14.1. Study Design/Endpoints

The phase 2 study will evaluate the efficacy of enzalutamide and tivozanib in patients with mCRPC. The primary endpoint will be progression free survival (PFS), defined as the time from registration to the earlier of progression (radiographic or clinical) or death and, if censored, the date of last disease evaluation. Based on phase 3 data, the median PFS with enzalutamide alone in chemotherapy naive mCRPC is 14 months. The hypothesis is that the addition of tivozanib will significantly enhance efficacy. An improvement of 60% to a median PFS of 22.4 months will be considered worthy of further study. Assuming exponential distribution, this implies a hazard ratio (HR) of 0.625 relative to historical control (hazard rate from 0.0495 to 0.0309). Using a one-sample exponential test, there will be 80% power to demonstrate a 60% improvement at a one-sided Type 1 error rate of 10% with enrollment of 38 patients and 20 PFS events.

Because this combination has not been previously tested, a safety run-in will be conducted at the outset of the trial. After the first 3 patients are enrolled, accrual will be held until all three patients complete the first 1 month of treatment. Additionally, after a total of 10 patients are enrolled, these patients will be analyzed for safety and toxicity by the DSMC. If any treatment-related, expected or unexpected grade 3 or higher adverse events occur during the first month of treatment in the first 3 patients, or if the rate is >30% among the first 10 patients during the first month of treatment, further accrual will be halted for reconsideration of the appropriateness of the dosing schedules.

The table below gives the probability of observing 1 or more toxicities among the first 3 patients or 3 or more among the first 10 patients given different true underlying toxicity rates.

| True toxicity rate | 1% | 10% | 20% | 30% | 40% | 50% |
|--|--------|-------|-------|-------|-------|-------|
| Probability of Stopping Early (≥ 1/3) | 0.030 | 0.271 | 0.488 | 0.657 | 0.784 | 0.875 |
| Probability of Stopping Early (≥ 3/10) | <0.001 | 0.070 | 0.322 | 0.617 | 0.832 | 0.945 |

Thus, if the true underlying proportion of toxic events is 30% at the current dosing schedules, there is a greater than 60% chance of stopping early.

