2.1.2 Enzalutamide

Enzalutamide (MDV3100) is a small molecule antagonist of the androgen receptor (AR) that was originally selected based on its activity *in vitro* against prostate cancer cells that overexpressed androgen receptor⁴. In addition to binding tightly to AR, enzalutamide blocks nuclear translocation and DNA binding activity of AR, and furthermore has no known agonist activity against AR in contrast to previous generations of AR antagonists.

The rapid clinical development of enzalutamide is a testimony both to its clear efficacy against prostate cancer as well as its favorable tolerability profile. Clinical activity was observed at many dose levels, and the maximum tolerated dose for sustained treatment was 240 mg daily⁵. The dose chosen for subsequent trials was 160 mg daily. A randomized phase 3 trial of placebo versus enzalutamide in men with mCRPC was halted after an interim analysis demonstrated a

robust improvement in overall survival from 13.6 months to 18.4 months (P<0.0001)⁶. Treatment was well tolerated overall, and the most common reported side effects were fatigue and diarrhea. Early preclinical and clinical studies with enzalutamide raised a concern for an increased rate of seizures, and in the phase 3 trial, seizures were observed in 5 patients receiving enzalutamide (0.6%). Full efficacy and toxicity information is available in the package insert (http://www.astellas.us/docs/us/12A005-ENZ-WPI.pdf). Based on the results of the phase 3 trial, enzalutamide was approved by the US FDA for men with mCRPC previously treated with docetaxel chemotherapy.

Another phase 3 trial has studied the efficacy of enzalutamide in mCRPC patients who were chemotherapy naïve. This trial demonstrated a significant benefit in both primary endpoints, progression free and overall survival⁷. At 12 months, the rate of radiographic progression-free survival was 65% among enzalutamide-treated men, compared with only 14% among placebotreated men. All secondary endpoints similarly showed significant benefit to enzalutamide in this patient population.

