2.3 Rationale

Among the most exciting recent results in prostate cancer research has been the demonstration that enzalutamide improves overall survival in metastatic, castration resistant prostate cancer (mCRPC)⁶. Enzalutamide is a novel pure antagonist of androgen receptor (AR) that functions by binding with high affinity to AR, preventing AR translocation to the nucleus, and ultimately inducing apoptosis of tumor cells. In the pivotal phase 3 trial, median survival in men previously treated with chemotherapy for mCRPC increased from 13.6 months to 18.4 months with the addition of enzalutamide⁶. There were also significant improvements in progression free survival (PFS) and other efficacy endpoints, with a median PFS of 8.3 months. Treatment with enzalutamide was well tolerated, in line with generally held and validated beliefs that effective hormonal agents offer substantial improvements in risk/benefit profiles compared with cytotoxic chemotherapy. A phase 3 trial with enzalutamide in chemotherapy-naïve patients with mCRPC has been completed, with results not yet available. Novel hormonal agents such as enz, abiraterone and others are unequivocally central to the current treatment paradigm in mCRPC.

The role of antiangiogenic therapy in prostate cancer is less certain, and at this time remains investigational. Two recent phase 3 trials, with bevacizumab and sunitinib respectively, failed to demonstrate an overall survival benefit for men with mCRPC receiving antiangiogenic therapy^{10,11}. However, each of these trials did show significant improvement in PFS. In the bevacizumab trial, men treated with docetaxel and prednisone (DP) had median PFS of 7.5

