3. PARTICIPANT SELECTION

3.1 Eligibility Criteria

Participants must meet the following criteria on screening examination to be eligible to participate in the study:

- **3.1.1** Participants must have adenocarcinoma of the prostate that is metastatic or unresectable and for which standard curative options do not exist
- **3.1.2** Participants must have radiographic evidence of metastatic prostate cancer
- **3.1.3** Participants must have progressive disease despite ongoing androgen deprivation therapy (ADT) and castrate levels of testosterone, defined as castration resistant prostate cancer (CRPC)
- **3.1.4** Other than ongoing ADT, prior treatment with other hormonal agents such as antiandrogens or ketoconazole must have been stopped at least two weeks prior to enrollment

- **3.1.5** Participants may have received prior docetaxel-based chemotherapy for prostate cancer. Such chemotherapy must have been stopped at least three weeks prior to the first dosing in this study.
- 3.1.6 Male patients age ≥ 18 . Because no dosing or adverse event data are currently available on the use of enzalutamide or tivozanib in participants <18 years of age, children are excluded from this study.
- **3.1.7** Life expectancy of greater than 12 weeks
- **3.1.8** ECOG performance status ≤ 2
- **3.1.9** Participants must have normal organ and marrow function as defined below:
 - Absolute neutrophil count ≥ 1,500/mcL
 - Platelets $\geq 50,000/\text{mcL}$
 - total bilirubin $\leq 1.5 \times \text{ULN}$ (or $\leq 2.5 \times \text{ULN}$ for subjects with

asymptomatic Gilbert's syndrome)

- AST (SGOT)/ALT (SGPT) ≤ 2.5 X institutional upper limit of normal
- Creatinine $\leq 2x$ ULN
- Proteinuria < 3+ by urinalysis or urine dipstick
- **3.1.10** The effects of tivozanib and enzalutamide on the developing human fetus are unknown. For this reason, participating men must agree to use adequate contraception (hormonal or barrier method of birth control; abstinence) prior to study entry and for the duration of study participation.
- **3.1.11** Ability to understand and the willingness to sign a written informed consent document.

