3.2 Exclusion Criteria

Participants who exhibit any of the following conditions at screening will not be eligible for admission into the study.

- **3.2.1** Prior treatment with enzalutamide, TOK-001, or ARN-509. Prior therapy with abiraterone or orteronel is permitted, but must have been stopped a minimum of two weeks prior to study entry. Prior and/or concurrent treatment with bone-targeted therapy such as bisphosphonates or denosumab is permitted.
- **3.2.2** Participants who have received more than two prior chemotherapy regimens for metastatic CRPC
- **3.2.3** Participants may not be receiving any other investigational anticancer agents

- **3.2.4** Participants with known brain metastases
- **3.2.5** History of allergic reactions attributed to compounds of similar chemical or biologic composition to tivozanib or enzalutamide
- **3.2.6** Radiotherapy or minor surgical procedure within 2 weeks, or major surgical procedure within 4 weeks prior to administration of first dose of study drug; inadequate recovery from prior surgical procedure
- **3.2.7** Any history of seizure or condition that may predispose to seizure
- **3.2.8** Significant cardiovascular disease, including
 - Uncontrolled hypertension: systolic blood pressure > 140 mmHg and/or diastolic blood pressure > 90 mmHg documented on 2 consecutive measurements taken at least 24 hours apart;
 - Myocardial infarction, severe angina, or unstable angina within 6 months prior to administration of first dose of study drug;
 - History of Class III or IV congestive heart failure, as defined by the New York Heart Association;
 - History of serious ventricular arrhythmia (ie, ventricular tachycardia or ventricular fibrillation):
 - Cardiac arrhythmias requiring anti-arrhythmic medications (except for atrial fibrillation that is well-controlled with anti-arrhythmic medication; and/or
 - Coronary or peripheral artery bypass graft within 6 months of screening
- **3.2.9** Non-healing wound, bone fracture or skin ulcer
- **3.2.10** Active peptic ulcer disease, inflammatory bowel disease, ulcerative colitis, or other gastrointestinal condition with increased risk of perforation; history of abdominal fistula, gastrointestinal perforation, or intra-abdominal abscess within 4 weeks prior to administration of first dose of study drug
- **3.2.11** Serious/active infection or infection requiring parenteral antibiotics

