7.2.4 Availability

Enzalutamide is a commercially available product, and is indicated for the treatment of men with mCRPC following failure of chemotherapy. For the purposes of this study, the product will be billed to patients' insurance.

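### The 80% power in Section 14.1 holds only for chemotherapy-naive men, but men with prior chemotherapy are eligible; the shortfall depends on their share and on benchmarks whose PFS definitions are not stated

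*Combined protocol and SAP*

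**What the plan says.** Section 14.1 describes a phase 2 study in patients with mCRPC. The null is one historical median: "Based on phase 3 data, the median PFS with enzalutamide alone in chemotherapy naive mCRPC is 14 months". A 60% improvement, to 22.4 months (HR 0.625), is the target. With 38 patients and 20 PFS events, "there will be 80% power to demonstrate a 60% improvement at a one-sided Type 1 error rate of 10" per cent.

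Eligibility is wider than that benchmark. Section 3.1.5 says "Participants may have received prior docetaxel-based chemotherapy for prostate cancer". Section 3.2.2 excludes only "Participants who have received more than two prior chemotherapy regimens for metastatic CRPC", so one or two regimens are allowed. Section 7.2.4 adds that "Enzalutamide is a commercially available product, and is indicated for the treatment of men with mCRPC following failure of chemotherapy".

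For the phase 3 trial in men already treated with chemotherapy, Section 2.3 reports enzalutamide results "with a median PFS of 8.3 months". The same section says the chemotherapy-naive phase 3 trial "has been completed, with results not yet available", yet Section 2.1.2 reports that trial: "At 12 months, the rate of radiographic progression-free survival was 65% among enzalutamide-treated men".

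Sections 14.1 to 14.4 have no limit on post-chemotherapy men, no stratification by prior chemotherapy, no blended null and no chemotherapy-naive analysis set for the primary endpoint.

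**The concern.** A one-sample test compares the enrolled patients with a fixed historical hazard, so its error rates mean what they say only if that hazard describes the patients enrolled. Here the null hazard belongs to chemotherapy-naive men, while the eligible population includes men for whom the protocol's own background gives a much shorter median. Such men pull the pooled PFS down whatever tivozanib does. A combination that truly improves PFS by 60% in every man could then miss the target, and a regimen worth taking forward could be dropped.

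Neither the 14 nor the 8.3 months comes with a PFS definition, and Section 14.1 gives no citation for the 14. Section 9.1.4 counts radiographic progression, clinical progression and death. A reader cannot tell whether either benchmark measures the same thing.

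**Working it through.** **Inputs.** From Section 14.1: naive median 14 months, HR 0.625, one-sided alpha 10%, 38 patients, 20 events. From Section 14.2: 21 months of accrual. From Section 2.3: 8.3 months after chemotherapy. Assumed, because the documents do not give them: the post-chemotherapy share; alternative post-chemotherapy medians of 10 and 12 months; an alternative naive median of 16 months; exponential PFS in each group; and the same HR of 0.625 in both groups.

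**Hazards.** ln 2/14 = 0.0495 per month; ln 2/8.3 = 0.0835 per month.

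**Reproducing the plan's figure.** Let E = null hazard × total follow-up time. At 20 events under the null, E follows Gamma(20, 1), whose 90th percentile is 25.90; reject if E > 25.90. Power = P(Gamma(20) > 25.90 × 0.625) = 79.9%. The stated 80% is right for a wholly chemotherapy-naive trial.

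**Pooled medians with 14 and 8.3 months at a 20% share.** With no tivozanib effect, solving 0.8·exp(−0.0495t) + 0.2·exp(−0.0835t) = 0.5 gives t = 12.5 months. With HR 0.625 it is 20.1 months. Since 20.07/14 = 1.43, a true 60% gain looks like 43% over the 14-month null.

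**Simulation of the planned test** (200,000 trials per case, uniform 21-month accrual, analysis at the 20th event, each man post-chemotherapy with the given probability). Entries are type I error / power.

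| Naive median | Post-chemo median | 10% share | 20% share | 30% share |
|---|---|---|---|---|
| 14 | 8.3 | 6% / 73% | 4% / 64% | 2% / 55% |
| 14 | 10 (assumed) | 7% / 75% | 5% / 71% | 4% / 65% |
| 14 | 12 (assumed) | 9% / 78% | 8% / 76% | 7% / 74% |
| 16 (assumed) | 8.3 | 17% / 86% | 10% / 79% | 6% / 69% |

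With 42 patients instead of 38, the 14/8.3 power is 63.9% at a 20% share and 54.6% at 30%, so the planned inflation does not change the picture.

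**The naive benchmark.** An exponential with a 14-month median gives exp(−0.0495 × 12) = 55% progression-free at 12 months, against the 65% radiographic figure in Section 2.1.2. Read as exponential, 65% implies 12 × ln 2/(−ln 0.65) = 19.3 months. With 19.3 and 8.3 months at a 20% share, the planned test would have 28% type I error and 91% power. The endpoints differ, so this shows sensitivity, not an error in the 14 months.

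**A null matched to prior chemotherapy.** Take E = sum over strata of (stratum null hazard × follow-up time), compared with 25.90. If 14 and 8.3 both hold, this restores about 10% / 80% at every share. At a 20% share, its type I error becomes about 14% to 15% if the post-chemotherapy median is really 10, about 20% if it is really 12, and about 21% if the naive median is really 16.

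**The case against.** The strongest reply is that neither the size nor the direction is settled. No section gives the expected share; the indication in Section 7.2.4 supports a share above zero, not 20% or 30%. The 8.3 months may not fit: its PFS is undefined, and Section 3.1.5 allows docetaxel at any stage of prostate cancer, so some of these men may have had it before castration resistance. With 12 months in place of 8.3 the loss is only a few points. With a naive median of 16 and a 20% share, the test is back at about 10% / 79%. Section 14.1 also labels its benchmark openly as chemotherapy naive, and under its own 14-month figure the mismatch makes the test conservative.

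All of that stands, and it rules out two readings that a reader might infer. One is that the trial's power simply is 64% or 55%; those values need a particular share, the 8.3-month median and a common HR. The other is that false positives are inflated. That would need a naive median longer than 14 months, and the 65% radiographic figure does not establish one, because this trial's PFS also counts clinical progression.

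The words in Section 2.3 about unavailable results read as stale background, since Section 2.1.2 reports the trial and the reference list dates it 2014.

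What the reply does not remove is that the label on the benchmark is never carried through to the power statement, which is given for the whole mCRPC population.

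**Conclusion.** The concern holds as a conditional one. The arithmetic behind the 80% is correct, but it describes a trial in chemotherapy-naive men, and Sections 3.1.5 and 3.2.2 define a broader one. If the naive median is 14 months and post-chemotherapy men do worse on this trial's endpoint, any share above zero takes power below 80%. For shares of 10% to 30% it lies between about 78% (median 12, 10% share) and 55% (median 8.3, 30% share). Type I error is below 10% throughout that range, so the harm is lost power and a positive result is not undermined by the mismatch. This rests on exponential PFS, HR 0.625 in every man, 38 patients and analysis at 20 events. If the naive median is longer than 14 months, type I error can exceed 10% (17% with 16 months and a 10% share), which is why the source and definition of the benchmark matter as much as the mix. It should be fixed; confidence in the size is medium.

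**What to change.** 1. In Section 14.1, say that the 10% and 80% apply to chemotherapy-naive men, and give power by post-chemotherapy share and median. For shares of 10%, 20% and 30%: about 73%, 64% and 55% with 8.3 months; 75%, 71% and 65% with 10; 78%, 76% and 74% with 12.
2. State the source and PFS definition of the 14 and the 8.3 months, and whether each matches Section 9.1.4. Update the outdated sentence in Section 2.3.
3. Keep the 14-month test as primary. Report the enrolled mix, and PFS, by prior chemotherapy for mCRPC.
4. Only after step 2, add a labelled sensitivity analysis using the matched E above with the confirmed benchmarks, compared with 25.90 at 20 events. Vary both medians. Show men whose only docetaxel came before mCRPC in each stratum in turn, since the documents give no benchmark for them.

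The matched test should not become primary unless both benchmarks are confirmed and a dated amendment is made before any PFS outcome is examined. That route may be closed: the calendar in Section 8 provides for Cycle 46, which starts 45 × 28 = 1,260 days (about 41 months) into treatment, against 21 + 6 = 27 months of planned accrual and follow-up.

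The cost is text changes, a source check and one extra analysis, with no added patients or events. Section 12.1 lists forms but not their fields, so confirm that the setting of prior chemotherapy is recorded. The stated power will look less favourable, and the sensitivity analysis is only as good as its benchmarks. It also leaves prior abiraterone or orteronel (allowed by Section 3.2.1) unadjusted, because the documents give no benchmark for those men.

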1.1 Study Design

We plan to conduct a single arm, open label, combination study with tivozanib and enzalutamide (enz) in men with metastatic castration resistant prostate cancer (mCRPC). All men will receive standard dosing of each drug, with tivozanib administered at 1.5 mg once daily for 3 weeks followed by a one-week break, and enzalutamide taken continuously at 160 mg once daily. Both will be orally administered. A single dose reduction of tivozanib will be permitted, if necessary, to 1.0 mg daily. Patients will continue on treatment until they experience objective or clinical disease progression, or unacceptable toxicity.

Because this combination has not been previously tested, a safety run-in will be conducted at the outset of the trial. While waiting for the first 3 patients to complete one month of treatment, no more than 10 total patients may be enrolled. These patients will be analyzed for safety and toxicity. If any treatment-related, expected or unexpected grade 3 or higher adverse events occur during the first month of treatment in the first 3 patients, or if the rate is >30% among the first 10 patients during the first month of treatment, further accrual will be halted for reconsideration of the appropriateness of the dosing schedules.

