14.2. Sample Size/Accrual Rate

A total of 38 evaluable patients will be needed to meet the primary endpoint. Sample size will be inflated to 42 patients to account for unevaluable patients. Accrual duration is expected to be

21 months (accrual rate of 2 patients per month) with additional follow-up of 6 months required to reach full event information.

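### The 10-patient safety analysis is triggered by the 10th enrolment, but its halt rule is defined on a completed first month of treatment

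*Combined protocol and SAP*

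**What the plan says.** Sections 5 and 14.1 describe the run-in in the same words. For the first 3 men there is both an accrual hold and a completion condition: "After the first 3 patients are enrolled, accrual will be held until all three patients complete the first 1 month of treatment". The next sentence moves to 10 men: "Additionally, after a total of 10 patients are enrolled, these patients will be analyzed for safety and toxicity by the DSMC". It contains no hold, no minimum follow-up and no data cut-off.

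Accrual is to be halted if any related grade 3 or higher event occurs in month 1 among the first 3, "or if the rate is >30% among the first 10 patients during the first month of treatment". Section 14.1 then tabulates the probability of stopping, with the second row based on "3 or more among the first 10 patients".

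Section 1.1 describes the run-in differently: "While waiting for the first 3 patients to complete one month of treatment, no more than 10 total patients may be enrolled". It says these patients will be analysed but gives no timing for the analysis.

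Section 14.2 plans accrual of 2 patients per month and a total of 38 evaluable men, inflated to 42.

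**The concern.** The trigger and the endpoint do not match. A rate of events during month 1 among 10 men is known only when all 10 have passed month 1 or had an event, yet the stated trigger is a headcount. Because completion is spelled out for the first 3 and missing one sentence later for the 10, a reader can take enrolment alone to be enough.

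An analysis at the trigger would include men who are still inside their window. With no rule for those men, the natural default is to count them as event-free in a denominator of 10. The rule would then halt accrual less often than the table implies.

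This is the last numeric toxicity rule before a further 28 to 32 men (38 − 10 to 42 − 10) receive a combination that the protocol describes as untested.

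**Working it through.** **Inputs.** Accrual of 2 per month (14.2); month-1 window and >30% rule (5 and 14.1); at least 3 of 10 in the table (14.1). Assumptions added here: evenly spaced enrolment, treatment starting at enrolment, constant hazard within month 1, data cut at the 10th enrolment, and open windows counted as event-free.

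**1. The plan's own table.** With p the true rate, row 1 is 1 − (1 − p)³ and row 2 is P(Bin(10, p) ≥ 3). At p = 0.3 these give 0.657 and 0.617, as printed. The other cells also reproduce (0.833 against a printed 0.832 at 40%, a rounding difference). Row 2 is a binomial on 10 men, so it assumes that every one of them is fully observed.

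**2. Follow-up at the trigger.** Patient i has (10 − i) × 0.5 months: patient 8 has 1.0, patient 9 has 0.5, patient 10 has 0. So 2 of 10 are incomplete. The hold after patient 3 does not change this, because it comes before patients 4 to 10 enrol.

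**3. Second look taken alone, as in the table, at p = 0.3.** Eight men are complete. Patient 9 shows an event with probability q = 1 − 0.7^0.5 = 0.163, and patient 10 with probability 0.

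- Text rule (>30% of 10 means at least 4). Full data: P(Bin(10, 0.3) ≥ 4) = 0.350. At the trigger: P(Bin(8, 0.3) ≥ 4) + q × P(Bin(8, 0.3) = 3) = 0.194 + 0.163 × 0.254 = 0.236.
- Table rule (at least 3). Full data: 0.617. At the trigger: 0.448 + 0.163 × 0.296 = 0.497.

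At p = 0.4 the text rule falls from 0.618 to 0.469.

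**4. Halting at either look, text rule.** The probability is [1 − (1 − p)³] + (1 − p)³ × S, where S is the chance of at least 4 events among men 4 to 10. With full data S = P(Bin(7, p) ≥ 4). At the trigger, S is computed from 5 complete men plus patient 9 at half a month.

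| True rate | S, full | S, at trigger | Either look, full | Either look, at trigger |
|---|---|---|---|---|
| 30% | 0.126 | 0.052 | 0.657 + 0.343 × 0.126 = 0.700 | 0.657 + 0.343 × 0.052 = 0.675 |
| 40% | 0.290 | 0.139 | 0.784 + 0.216 × 0.290 = 0.847 | 0.784 + 0.216 × 0.139 = 0.814 |
| 50% | 0.500 | 0.279 | 0.875 + 0.125 × 0.500 = 0.938 | 0.875 + 0.125 × 0.279 = 0.910 |

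**5. Sensitivity.** An event time uniform over the month gives 0.232 instead of 0.236 in step 3. With Poisson arrivals at 2 per month, about 3 of 10 men are incomplete on average, and the chance of 2 or more is 86%. Any lag from registration to first dose raises the count. Under the Section 1.1 wording, up to 7 of 10 could be incomplete. If the analysis waits a month or more after the 10th man starts treatment, all windows are closed and the loss is zero.

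**The case against.** The strongest reply is that the text does not fix the analysis on the day the 10th man enrols. It says the analysis comes after that enrolment, which is compatible with waiting. It also does not say that men inside their window count as event-free. The halt condition is worded as a standing rule on the full first month of the first 10 men, so a late event in patient 10 would still meet it. Section 12.2 has the committee review toxicity quarterly or more often, and Section 14.3 has toxicity monitored in all treated men. Under Section 12.1, adverse event forms are due within 10 days of the end of a cycle, so a same-day snapshot is an unlikely picture of the data flow.

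Most of this stands, and it limits the finding. A reader might infer that two men cannot have finished month 1 and that the rule is therefore under-counted. The documents permit that outcome but do not prescribe it. A reader might also infer from S in the table above that the second look loses about half its ability to halt. That ratio applies only to trials that have already passed the first look with 0 of 3. Taken alone at a 30% rate, the second look loses about a third (0.350 to 0.236), and the run-in as a whole loses about 2.5 points.

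The reply does not supply the missing condition. A quarterly calendar neither guarantees a closed window nor prevents an early look. Waiting with no stated hold lets about 2 more men enrol per month. The plan does not choose between these.

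**Conclusion.** The concern holds as a mismatch between a stated trigger and its own endpoint, with a conditional effect. If the 10-patient analysis is run at the trigger, under even accrual and with open windows counted as event-free, 2 of 10 men are incomplete. The second look is then weaker under either threshold. The run-in as a whole loses about 2.5 to 3.3 percentage points at true rates of 30% to 50% under the text rule, because the first look does most of the stopping. The loss is zero if the committee waits for month 1 to close.

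The unreconciled threshold matters more than the timing. At a 30% rate, at least 4 of 10 gives 0.350 and at least 3 of 10 gives 0.617, even with complete data. The statement in Section 14.1 of a better than 60% chance of stopping, as far as it rests on the second row, needs both the table's threshold and a completed window. An amendment is still worthwhile, because this is the last numeric toxicity rule in the plan and the correction is small.

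**What to change.** In Sections 5 and 14.1, and aligned in Section 1.1:

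- State that the 10-patient analysis is done once each of the first 10 patients has completed the first month of treatment or had a qualifying event.
- State that the halt rule applies as soon as its limit is crossed, without waiting for the remaining windows to close.
- State whether accrual continues between the 10th enrolment and the committee's decision.
- Reconcile the >30% wording with the at least 3 of 10 row of the table, and recompute that row if needed. The amendment should not write in a fixed event count before this is settled.
- Reconcile Section 1.1, which lets up to 10 men enrol while the first 3 are observed, with the hold after 3 in Sections 5 and 14.1.

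The cost is a few sentences in one amendment. The analysis moves about one month later than the 10th enrolment, with about 2 further men enrolled in that time if accrual stays open at the planned rate. Applying the rule as soon as its limit is crossed avoids delay when enough events have already occurred.
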